5. STATISTICAL ANALYSES

5.1. Subject Information

Subject information will be tabulated using the FAS. No inferential testing will be performed nor will p-values be provided.

Subject information will be tabulated with descriptive statistics per treatment group and overall.

5.1.1. Demographic and Baseline Disease Characteristics

Summaries will also be provided by stratum (3 levels; nintedanib, pirfenidone, or neither). The following parameters will be considered:

- Date of ICF signature (listed only)
- Sex
- Age at signing the ICF (years)
- Age, categorized (years):
 - $40 \leq \text{age} < 50$
 - $50 \leq \text{age} < 60$
 - $60 \leq \text{age} < 70$
 - $\text{age} \geq 70$
- Race and ethnicity
- Height at baseline (cm)
- Weight at baseline (kg)
- Body mass index (BMI) at baseline (kg/m^2) = $\frac{\text{weight (kg)}}{\text{height}^2 (\text{m}^2)}$
(BMI will not be recalculated if already available in the database)
- BMI, categorized (kg/m^2):
 - $\text{BMI} \leq 18.5$

- $18.5 < \text{BMI} \leq 25.0$
- $25.0 < \text{BMI} \leq 30.0$
- > 30.0
- Baseline systolic and diastolic blood pressure and heart rate
- Baseline alcohol status: no, yes (“Does the patient drink alcohol?”)
- Baseline smoking status: nonsmoker, current smoker, ex-smoker
- Duration of IPF (years) = $\frac{(\text{date of first intake of study drug}) - (\text{date of initial diagnosis})}{365.25}$. If the date of initial diagnosis is incomplete, then the following rules will be applied: Missing day: use the first of the month. Missing month: use January.
- Duration of IPF, categorized (years):
 - duration < 0.5
 - $0.5 \leq \text{duration} < 1$
 - $1 \leq \text{duration} < 2$
 - $2 \leq \text{duration} < 3$
 - duration ≥ 3
- Baseline background SOC:
 - currently taking pirfenidone
 - currently taking nintedanib
 - never took pirfenidone or nintedanib
 - stopped taking pirfenidone and/or nintedanib
- Baseline spirometry:
 - FVC (mL)
 - percent predicted FVC (%)
 - forced expiratory volume in 1 second (FEV₁) (mL)
 - percent predicted FEV₁ (%)
 - FEV₁/FVC ratio
 - forced expiratory flow between 25% and 75% of exhaled volume (FEF₂₅₋₇₅) (mL/s)
- Other baseline efficacy measures:
 - SGRQ total score and domains:
 - symptoms (assessing the frequency and severity of respiratory symptoms),
 - activity (assessing the effects of breathlessness on mobility and physical activity),
 - impact (assessing the psychosocial impact of the disease).
 - 6MWT distance
 - ██████████
- DLCO (corrected for Hb)

5.1.2. Baseline Physical Examination

A frequency tabulation per body system of the baseline physical examination results, categorized as normal/abnormal, will be provided by treatment group and overall.

5.1.3. Disposition Information

The following tabulations will be provided, by treatment group and overall:

- The number of subjects screened, randomized (treated and not treated), not-randomized and the number (percent) of subjects in each analysis set as defined in Section 3.1.
- The number (percent) of subjects who completed/discontinued the study/treatment and the reasons for discontinuation. This table will also be provided by stratum.
- The number (percent) of subjects per analysis window as defined in Section 3.3.3.
- Number (percent) of subjects randomized per country and investigator.

In addition, the following listings will also be provided:

- Subject identification and randomization (country, site number, investigator, subject number, randomization number, planned and actual randomization group and stratum, with flags for discrepancies).
- Subjects excluded from the FAS and the reason for exclusion.
- Date of the earliest ICF signed for this study and date of last scheduled visit performed in this study.

5.1.4. Protocol Deviations and Eligibility

Major protocol deviations are determined and recorded while the study is ongoing, and the list is finalized prior to database lock (and unblinding). For more details, please refer to the Protocol Deviations Plan.

The number (percent) of subjects with major protocol deviations will be tabulated, overall and per class of deviation, by treatment group and overall.

All available information concerning major protocol deviations, violations on eligibility criteria, and subjects not treated will be listed. The major protocol deviations leading to exclusion from the Per-Protocol Analysis Set (see Section 3.1.4) will be flagged.

5.1.5. Medical History and Concomitant Diseases

Frequency tabulations per system organ class and preferred term will be provided for the medical history findings (i.e. condition no longer present at the start of the study) as well as for the concomitant diseases (i.e. conditions present at the start of the study).

5.1.6. Prior and Concomitant Therapies

5.1.6.1. Coding of Reported Terms

All prior and concomitant therapy terms will be coded in the database using the World Health Organization drug coding dictionary.

5.1.6.2. Classification of Therapies

All prior and concomitant therapy records will be categorized as follows, considering their date and flags indicating the relative timing versus study (drug) start or end (e.g. before, after, ongoing):

- Prior only: when the record ended before the first dose of IMP.
- Concomitant only: when the record started on or after the first dose of IMP.
- Prior and concomitant: when the record started before the first dose of IMP, and ended on or after this point, or continued.

Records without a start date are assumed to have started before the date of first study drug administration. Records without an end date are assumed to be ongoing.

When the start or end date of the prior and concomitant therapy records are incomplete (and no flags indicating relative timing are available), the date of first IMP administration will be considered to the same level of information provided by these incomplete dates to categorize the timing of these records. This means that a record only having month and year will be categorized comparing only to the month and the year of the date of first IMP administration. If the start date is unknown but the medication is flagged to have started prior to the first dose of IMP, this information will be taken into account.

5.1.6.3. Calculation of Relative Days

For both the start and the end dates of the concomitant therapy records, their day relative to the day of first study drug administration will be calculated as described in Section 4.3.1.

5.1.6.4. Presentation of Results

A frequency tabulation per treatment group and overall of the Anatomical Therapeutic Classification (ATC) classes level 4 by therapeutic subgroup (ATC level 2) and generic term of the prior medications (defined as ‘prior only’ and ‘prior and concomitant’) will be provided as well as of the concomitant medications (defined as ‘concomitant only’ and ‘prior and concomitant’).

Additional tables will be provided for respiratory-related concomitant and prior medications. The definition of respiratory-related medications will be provided in a separate document before unblinding for the final study report.

A frequency table per treatment group, summarizing the IPF SOC intake during the study, of the number and percentage of subjects with the following:

- Baseline SOC pirfenidone:
 - Stable dose until study end date
 - Reduced dose at least once
 - Temporarily stopped at least once
 - Permanently stopped and started nintedanib
 - Permanently stopped (without starting nintedanib)
- Baseline SOC nintedanib:
 - Stable dose until study end date
 - Reduced dose at least once
 - Temporarily stopped at least once
 - Permanently stopped and started pirfenidone
 - Permanently stopped (without starting pirfenidone)
- Baseline SOC neither:
 - Stable until study end date
 - Started nintedanib or pirfenidone and permanently stopped (without restarting other SOC)
 - Started nintedanib or pirfenidone and temporarily stopped (i.e. period without any SOC) at least once
 - Started nintedanib or pirfenidone and continued until study end date (includes subjects that switch SOC without temporary stop)

Note: these categories should be counted in a worst-case manner i.e. a subject appears only once in one of the categories (in the order as specified above with “permanent stop” or “starting SOC” as the worst cases).

In addition, a listing will be provided of the subjects who had any change in IPF SOC medication (pirfenidone, nintedanib or neither) during the treatment period compared to baseline e.g. switching between nintedanib and pirfenidone, starting pirfenidone/nintedanib, stopping pirfenidone/nintedanib, down-titration or up-titration of pirfenidone/nintedanib. All SOC therapy records are to be included.

5.1.7. Exposure to Study drug and Compliance

5.1.7.1. Derivation Rules

Derived Parameters: Extent of Exposure to Study Drug

- *Total treatment duration* (days) = last study drug administration date – first study drug administration date + 1 day.
- *Total treatment duration, excluding days off study drug*: Number of days with any study drug administration.

- *Total treatment duration, fully compliant* (days): Number of days with study drug administration of exactly 2 capsules.

Derived Parameters: Compliance

Study drug compliance is defined by the planned treatment dosage (100 mg q.d.; 2 tablets of 50 mg per day) without taking into account potential down-titrations (as allowed by the protocol).

- *Overall compliance (%)* = $100 \times \frac{\text{number of capsules actually used}}{\text{number of capsules that should have been used}}$ (according to randomization)
- *Percent days with any intake (%)* = $100 \times \frac{\text{total treatment duration, excluding days of drug}}{\text{total treatment duration}}$
- *Percent days fully compliance (%)* = $100 \times \frac{\text{total treatment duration, fully compliant}}{\text{total treatment duration}}$

5.1.7.2. Presentation of Results

Summary statistics per treatment group and overall will be provided for each compliance and extent of exposure parameter. Frequency tables will be provided for the compliance parameters, using the following categories: <80%; $80\% \leq x < 100\%$; 100%; $100\% < x \leq 120\%$; > 120%.

A listing will be provided of the subjects who took incorrect study medication (GLPG1205 instead of placebo, or vice versa) for at least part of the treatment period, all GLPG1205/placebo records are to be included to provide an overview of the amount of cross-treatment relative to the total treatment period.

In addition, a listing of the subjects who had their study medication down-titrated or interrupted for at least part of the treatment period will be provided. All GLPG1205/placebo records are to be included to provide an overview of the amount of down-titration/interruption relative to the total treatment period.

Finally, a listing of the subjects receiving investigational product from specific batches, where more than one batch was used (showing the batch numbers of the investigational products actually used, including the expiration dates) will also be provided.

5.2. Efficacy Analyses

Efficacy analyses will be performed on the FAS, excluding all data collected after lung transplant. To investigate the impact of non-compliance and protocol violators a Per-Protocol analysis will also be performed for the primary endpoint, if at least 10% of the subjects are omitted from the Per-Protocol Analysis Set.

Tabulations will be shown per treatment group.

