12. Any other clinical condition or circumstance that in the opinion of the investigator may make him or her unsuitable for inclusion or unable to complete the study or comply with study procedures and requirements.
13. Criterion modified per amendment.
 - 13.1 Moderate to severe hepatic impairment (Child-Pugh B or C) and/or abnormal liver function test (LFT) at screening, defined as aspartate aminotransferase (AST) and/or alanine aminotransferase (ALT) and/or bilirubin 1.5x and/or gamma glutamyl transferase (GGT) 3x upper limit of normal (ULN) range. Retesting is allowed once for abnormal LFT.
14. Criterion modified per amendment.
 - 14.1 Abnormal renal function defined as estimated creatinine clearance <30 mL/min using Cockcroft-Gault equation. Retesting is allowed once.
15. Criterion modified per amendment.
 - 15.1 Underwent major surgery within 3 months prior to screening or who has major surgery planned during the study period. Note: being on a lung transplant list is allowed.
16. Hemoglobin level <10 g/dl. Retesting is allowed once.
17. Criterion modified per amendment.
 - 17.1 Subject participating in a drug, device or biologic investigational research study, concurrently with the current study, within 12 weeks or 5-half-lives of the agent, whichever is longer, prior to screening, or prior participation in an investigational drug antibody/biologic study within 6 months prior to screening.
18. Criterion modified per amendment.
 - 18.1 Use any of the following therapies within 4 weeks before screening and during screening, or planned during the study:
 - a. Warfarin
 - b. Imatinib
 - c. Endothelin receptor antagonists (e.g. ambrisentan, bosentan and macitentan)
 - d. Azathioprine
 - e. Cyclophosphamide
 - f. Cyclosporine A
 - g. Methotrexate
 - h. Sildenafil
 - i. Prednisone at steady dose >10 mg/day or equivalent
19. Criterion modified per amendment.

- 19.1 Use any of the following therapies within 5 half-lives before screening and during screening, or planned during the study
- medications which are known BCRP substrates (see [Appendix 5](#))
 - medications which are known dual CYP3A4 and CYP2C19 inhibitors (see [Appendix 8](#))
 - medications which are known to be CYP3A4 or CYP2C19 strong inducers (see [Appendix 9](#))
20. Current alcohol or substance abuse in the opinion of the investigator.

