7.3.4. Analyses of Efficacy Parameters

All efficacy parameters (spirometry, clinical endpoints, quality of life, [REDACTED]) will be analyzed descriptively in the full analysis set unless otherwise specified.

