2.2.3. Other Endpoints

2.2.4. Adjudication

The following endpoints will be adjudicated by the clinical endpoint adjudication committee (CEAC):

- Mortality: all-cause and respiratory-related (2 separate endpoints)
- Hospitalization: all-cause and respiratory-related (2 separate endpoints)

Adjudicated endpoints will be used in the time-to-event analyses described in Section 5.2.3.1 and not the corresponding investigator-reported events. Consistency with the investigator-reported information will be investigated.

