3.4.1.3. Censoring of Time-to-Event Data

Subjects who do not report the event at the moment of the analysis, are censored at the date of last contact. The date of last contact is defined as the latest date collected in the CRF from the date of death, visit or assessment dates, AE dates, concomitant treatment dates, drug intake dates or lab test dates and trial completion date.

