5.2.3. Secondary Endpoints

5.2.3.1. Time to Major Events

A time to (first) event analysis will be conducted for major events, defined as

- Death (all-cause and respiratory-related)
- Hospitalization (all-cause and respiratory-related)

Deaths and hospitalizations will be adjudicated by the CEAC. The analysis will be based on the results from the adjudication, not on the investigator-reported information. Differences will be investigated and listed, if any.

The number and proportion of subjects with an event during the study will be summarized per treatment group. Treatment effect on time to first event will be assessed using the log-rank test. In addition, time to first event will be graphically displayed and tabulated (at each planned time point as described in Section 3.3.3, Week 2, Week 4, etc, and last available time point) per treatment group using Kaplan-Meier estimates.

In addition, for all-cause hospitalization and all-cause mortality a frequency table will be provided for the event classification categories as determined by the CEAC. These categories are described in the CEAC charter.

Censoring

Time-to-event endpoints are defined from the date of first dose of study medication.

If the subject did not have an event, the time to event will be censored at the last contact date, as defined in Section 3.4.1.3.

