5.5. Changes to the Planned Analyses, Not Covered by Protocol Amendments

[REDACTED]

Data after lung transplant will be excluded from all efficacy analyses.

[REDACTED]

In addition to descriptive statistics, ANCOVA models were included for the analysis of 6MWT distance, SGRQ score [REDACTED]

If changes are needed after unblinding these will be documented in the CSR with an explanation for the reason for the change.

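### As worded, the SAP's lung-transplant exclusion also removes post-transplant deaths from endpoints defined as all-cause, and the censoring date for such subjects is not stated

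*SAP*

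**What the plan says.** - **The exclusion.** SAP 5.2 restricts the efficacy analyses to the full analysis set, "excluding all data collected after lung transplant". SAP 5.5 lists this among changes that no protocol amendment covers: "Data after lung transplant will be excluded from all efficacy analyses". Neither sentence separates measurements from events.
- **Its reach.** Time to Major Events is SAP 5.2.3.1, inside the efficacy section. Protocol 7.3.4 also counts clinical endpoints among the efficacy parameters.
- **The endpoint.** Protocol 4.1.2 and SAP 2.2.2 define the secondary endpoint as time to the first major event, with death and first hospitalisation each taken as all-cause and as respiratory-related. Neither mentions transplant. SAP 2.2.4 has all-cause and respiratory-related mortality adjudicated as two separate endpoints and says that adjudicated endpoints feed the time-to-event analyses. SAP 5.2.3.1 adds a frequency table of adjudicated event categories for all-cause mortality.
- **Censoring.** Under SAP 5.2.3.1 a subject without an event is censored at last contact. SAP 3.4.1.3 defines that as "the latest date collected in the CRF from the date of death" and several other recorded dates. Transplant is not made a censoring date, a competing event or an endpoint event in the visible text.
- **Eligibility.** Protocol 4.3.3, criterion 15.1, notes that "being on a lung transplant list is allowed".

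**The concern.** For FVC, walk distance and SGRQ the exclusion is sensible: values measured with a transplanted lung do not describe the effect of study drug on the original disease. A death is different. It remains a death after transplant, and an endpoint labelled all-cause should count it. A rule that fits measurements has been worded so that it also covers events.

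Two things are at stake. The mortality summaries could omit a death that the protocol's definition includes. And two programmers could give the same subject different follow-up times, because the exclusion and the last-contact definition were not written to work together.

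**Working it through.** **No plan figure to reproduce.** The only design calculation (protocol 7.1) concerns FVC. The documents give no death rate, transplant rate or event count, so the point is settled by reading the rules together. The arithmetic shows scale only.

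**Step 1: follow one death through the rules.** A subject is transplanted and later dies.

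1. Time to death is an efficacy analysis (SAP 5.2.3.1; protocol 7.3.4).
2. Data after transplant leave all efficacy analyses (SAP 5.2, 5.5), so the death is not an event.
3. Without a countable event the subject is censored at last contact (SAP 5.2.3.1, 3.4.1.3).
4. If the exclusion also removes later dates from last contact, censoring falls at or before transplant. If it does not, censoring can fall on the date of death. The SAP does not choose.

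On both readings the death is lost. They differ only in the censoring date.

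**Step 2: which outputs are exposed.**

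- All-cause first-event composite: little exposed. The admission for the transplant starts on or before the day of the operation and will normally already be the event.
- All-cause and respiratory-related mortality taken separately, and the all-cause mortality table: exposed.
- Respiratory-related events: exposed if the transplant admission is not adjudicated as respiratory-related.
- The protocol 7.3.4.2 endpoint of a 10-point fall in % predicted FVC or death: exposed only if the general rule in SAP 5.2 governs it. Its handling is not visible in the SAP.

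**Step 3: size of one lost death.** With the 40 and 20 subjects of protocol 7.1: 1/20 = 5 percentage points in placebo; 1/40 = 2.5 points in GLPG1205.

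**Step 4: illustration on assumed data.** Take 40 versus 20 subjects followed to day 211, with deaths on day 120 (GLPG1205) and days 60 and 150 (placebo). One further subject is transplanted on day 100 and dies on day 110, 140 or 180. Survival is Kaplan-Meier at day 183. The log-rank statistic is (O − E)²/V for deaths only, on 1 degree of freedom.

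Worked case, placebo subject dying on day 110:

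- Death counted: survival = 19/20 × 18/19 × 17/18 = 85.0%. In the GLPG1205 arm O = 1, E = 40/60 + 40/59 + 40/58 + 39/57 = 2.7185, V = 0.8707, chi-square = 3.39, p = 0.066.
- Death dropped: survival = 19/20 × 17/18 = 89.7%. O = 1, E = 40/60 + 40/58 + 39/57 = 2.0405, V = 0.6523, chi-square = 1.66, p = 0.198.

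Ranges over the three death days:

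| Arm of transplanted subject | Handling of the death | Deaths in total | Week 26 survival, that arm | p |
|---|---|---|---|---|
| Placebo | counted | 4 | 85.0% | 0.066–0.069 |
| Placebo | dropped, censored at death date | 3 | 89.7–90.0% | 0.198–0.211 |
| Placebo | dropped, censored at transplant | 3 | 89.7% | 0.198 |
| GLPG1205 | counted | 4 | 95.0% | 0.454–0.467 |
| GLPG1205 | dropped, censored at death date | 3 | 97.4–97.5% | 0.211–0.217 |
| GLPG1205 | dropped, censored at transplant | 3 | 97.4% | 0.217 |

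Losing the event matters; the choice of censoring date hardly does. The p-value rises when the case is on placebo and falls when it is on GLPG1205.

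**The case against.** **The exclusion should be applied consistently.** A reader might infer that a subject transplanted on Day 80 who dies on Day 100 is credited as event-free to Day 100. The documents do not establish that. A death date recorded after transplant is itself data after transplant, so a consistent reading removes it from last contact as well. Listing the date of death in SAP 3.4.1.3 is also legitimate: a subject who dies of another cause must be censored somewhere in a cause-specific analysis. This objection stands against the event-free claim. It does not restore the lost death.

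**The defined endpoint is a first-event composite.** This largely stands for the all-cause version. SAP 5.2.3.1 also does not clearly specify a stand-alone log-rank test for mortality, so the p-values above do not measure harm to a clearly planned test. SAP 2.2.4 nevertheless sends separately adjudicated mortality to the time-to-event analyses, and the mortality table is explicit.

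**Deaths stay visible in the safety outputs.** True. SAP 5.3 carries no transplant exclusion, and SAP 5.3.1.7 tabulates treatment-emergent events leading to death and lists all adverse events leading to death. That limits the harm but leaves the efficacy endpoint inconsistent with its definition.

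**The case is improbable, and the rule is declared in advance.** Also true. The rationale for protocol Amendment 1 says that listing does not imply a high chance of transplant, planned major surgery is an exclusion, and the study is non-confirmatory (SAP 5.2.1). Text around the sentence in SAP 5.5 is redacted, so further transplant handling there cannot be ruled out.

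**Conclusion.** The point holds in a limited form. As written, the exclusion covers the death and hospitalisation endpoints, so a post-transplant death would be lost from an endpoint defined as all-cause, whichever censoring date is used. That date is itself unspecified.

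The effect is small. It rests on an assumed 0 or 1 affected subject, and it falls mainly on mortality taken separately, the all-cause mortality table and possibly the respiratory-related analyses. The primary FVC analysis is untouched.

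Two further inferences are not supported. The first is that the rule favours one treatment: mortality is understated in whichever arm holds the case, and the illustration moves both ways. The second is that censoring at transplant must be informative because transplant marks terminal disease. That may be argued clinically, but the documents do not say it and this conclusion does not need it.

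This is a minor wording correction, best made before unblinding.

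**What to change.** 1. In SAP 5.2 and 5.5, limit the exclusion to spirometry, 6MWT, SGRQ and similar measurements.
2. In SAP 5.2.3.1, state that adjudicated deaths and hospitalisations after lung transplant are counted, and add a sensitivity analysis that censors at transplant.
3. In SAP 3.4.1.3, align the last-contact definition: follow-up continues past transplant in the main time-to-event analysis and stops at transplant in the sensitivity analysis.

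The cost is a few sentences and one extra run of an existing analysis. No new data are needed and the FVC rule is unchanged. The small downside is that events after transplant partly reflect the transplant itself; the sensitivity analysis addresses this.
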